2.2 Analysis sets

The **Enrollment Set** includes all participants who signed the informed consent form (ICF) and are assigned participant numbers. This analysis set will be used to summarize the disposition of participants, pre-treatment adverse events (AEs) and counts of AEs during the on-treatment period.

The Full Analysis Set (FAS) comprises of all participants who received at least one dose of study treatment in the extension study. This analysis set will serve as the primary analysis set for all efficacy and safety analyses.

The Per-Protocol Set (PPS) is a subset of participants in the FAS with major protocol deviation (with impact). Patients with important PDs but without impact will be reported as PD and will be included in PPS.

The list of protocol deviation criteria will be provided in the edit check specification document. Please refer to [Table 5-1](#) for more details.

2.2.1 Subgroup of interest

Primary endpoint analysis for BCVA will be conducted using the following baseline BCVA and age categories:

- Baseline BCVA categories: < 55, 55-< 73, ≥ 73 letters read,
- Age categories: < 75, ≥ 75 years old.

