Key safety assessments	
 Monitoring of adverse events Ophthalmic examinations and imaging Vital signs (pulse and blood pressure) Pregnancy testing
Other assessments	Ocular Coherence Tomography Angiography
Data analysis	
The primary analyses will be conducted in the full analyses set with missing data imputed based on the last observation carried forward method.
 
Duration of the last interval with no disease activity up to Week 56 will be estimated using proportions with two-sided 95% Binomial Confidence Intervals and simultaneous Confidence Intervals obtained based on Goodman method (1965). The change in best corrected visual acuity from extension baseline at Week 52 and Week 56 will be estimated based on an analysis of covariance model with baseline best corrected visual acuity and age. The estimates of the change in best corrected visual acuity will be accompanied by two-sided 95% Confidence Intervals.
 
Additional analysis is planned to evaluate the impact of the COVID-19 pandemic and the q4w urgent safety measures on the primary and selected secondary endpoints.

Key words	Neovascular age-related macular degeneration, anti-VEGF, choroidal neovascularization, individualized treatment

1 Introduction

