12.4.2 Statistical model, hypothesis, and method of analysis

The average change in BCVA from extension baseline at Week 52 and Week 56 will be estimated in Analyses of Covariance (ANCOVA) with baseline age categories and baseline BCVA categories. The estimate of BCVA change will be accompanied by 95% CI.

The distribution of the last interval with no DA up to Week 56 will be described based on counts and proportions of participants at 4-week, 8-week, 12-week, 16-week, and 20-week intervals. The proportions will be accompanied by 95% Confidence Intervals (CI).

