2.3 Patient disposition, demographics and other baseline characteristics

Demographic and other extension study baseline data including disease characteristics will be summarized by appropriate descriptive statistics for all analyses sets. A listing will also be provided.

A baseline (of the extension study) disease characteristic table will be provided by treatment groups of the core study and overall, including:

- Primary diagnosis of nAMD, time since diagnosis of nAMD (days), whether nAMD is unilateral or bilateral and intraocular pressure (IOP).
- BCVA (as a continuous variable and using categories (< 55, 55-< 73, ≥ 73 letters read)),
- OCT angiography parameters – if collected.
- SD-OCT parameters (IRF, SRF, sub-RPE, CSFT (as a continuous variable and using categories (< 400, ≥ 400 μm)) and lesion type).
- CFP parameters (intra-retinal hemorrhage – central subfield, sub-retinal hemorrhage – central subfield, RPE atrophy – outer subfield, RPE atrophy – central subfield, fibrosis – inner subfield, fibrosis – central subfield).
- FA parameters (type of CNV, area of CNV within the lesion, CNV location, leakage from CNV).

Relevant medical histories and current medical conditions at baseline of the extension study will be summarized separately by system organ class and preferred term for the FAS.

Medical history/current medical conditions will be coded using the latest version of Medical Dictionary for Regulatory Activities (MedDRA) terminology available at the time of the analyses. The MedDRA version used for reporting will be specified in the clinical study report (CSR) and as a footnote in the applicable tables/listings.

Medical histories which started before the core study and are ongoing on Day 1 of the extension study will be recorded on the Medical History eCRF. Data collected for the Medical History

eCRF for the extension study will be presented by the treatment arm in the core study and overall. Columns will be included to identify if the event started before the core study, during the core study, or during the extension study; and if the event is ongoing or ended during the Extension study.

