2.5.2 Statistical hypothesis, model, and method of analysis

The average change in BCVA from baseline of the extension study at Week 52 and Week 56 will be estimated by an analysis of variance (ANOVA) with baseline age categories, baseline BCVA categories and treatment arm in the core study included as fixed effects. The estimate of BCVA change will be accompanied by the 95% CI.

For the analysis of durability, the first step is to identify the last (treatment) interval with respect to Week 56 for each participant, i.e. the last interval for which injections have occurred at both ends of this interval before/at Week 56. If there is disease activity at the end of the last interval, then the last interval will be shortened by 4 weeks, down to a minimum of q4w. Subjects who do not receive any injection (or only one injection) of study drug in the extension study will be excluded from this analysis. In case of any treatment interruption or permanent study treatment discontinuation, the imputation techniques as per the estimand framework in [Section 2.5.3](#) will be considered. Then, the proportion of participants with last interval of q4w, q8w, q12w, q16w, and q20w will be specified. These proportions will be referred as the distribution of the last interval.

The distribution of the last interval with no disease activity up to Week 56 will be described based on counts and proportions of participants at 4-week, 8-week, 12-week, 16-week, and 20-week intervals. These proportions will be accompanied by 95% CIs. The counts and proportions will be accompanied by 2-sided 95% CIs inferred based on binomial distribution for each endpoint and 2-sided 95% simultaneous CIs inferred using the Goodman method (Goodman 1965). The Goodman method is used for obtaining simultaneous CIs for the parameters of a multinomial distribution, for example for a multinomial endpoint (4-week interval, 8-week interval, 12-week interval, 16-week interval, and 20-week interval).

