2.6.2 Statistical hypothesis, model, and method of analysis

Counts and proportions for the endpoints describing durability, tolerability, and anatomical outcomes (i.e., number of visits with presence of IRF and/or SRF) will be accompanied by 2-sided 95% CI inferred based on binomial distribution for each endpoint and 2-sided 95% simultaneous CIs inferred using the Goodman method (Goodman 1965). The Goodman method is used for obtaining simultaneous CIs (better than single binomial CIs) for the parameters of a multinomial distribution, for example for a multinomial endpoint (4-week interval, 8-week interval, 12-week interval, 16-week interval, and 20-week interval). These analyses will be performed for all participants and within the two regimens.

For the analyses of functional and anatomical outcome (i.e., change in CSFT) the 95% CI will be inferred based on ANOVA analyses. The same analysis model as used for change from

baseline in BCVA will be used with the baseline BCVA categories replaced by baseline CSFT categories.

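### The secondary CSFT change model adjusts for baseline thickness only in categories, apparently one cut at 400 µm, so about half or more of any core-arm baseline difference can stay unadjusted although continuous CSFT is available

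*SAP*

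**What the plan says.** The primary BCVA model in SAP 2.5.2 is an ANOVA "with baseline age categories, baseline BCVA categories and treatment arm in the core study included as fixed effects". SAP 2.2.1 introduces the cuts with the statement "Primary endpoint analysis for BCVA will be conducted using the following baseline BCVA and age categories" and lists them: "Baseline BCVA categories: < 55, 55-< 73, ≥ 73 letters read" and "Age categories: < 75, ≥ 75 years old". Table 2-1 and the MMRM in SAP 2.5.4 use the same factors.

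For change in CSFT, SAP 2.6.2 takes over the BCVA model "with the baseline BCVA categories replaced by baseline CSFT categories". It does not say what those categories are. The only definition is in the list for the descriptive baseline table in SAP 2.3, a single split at 400 µm. That list also carries the continuous values: it has "BCVA (as a continuous variable and using categories", and CSFT is treated the same way.

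The protocol words the BCVA model in two ways. Its summary describes an "analysis of covariance model with baseline best corrected visual acuity and age", without mentioning categories. Section 12.4.2 specifies "Analyses of Covariance (ANCOVA) with baseline age categories and baseline BCVA categories", and the ANCOVA and mixed-model rows of Table 12-1 agree with it. For CSFT, protocol 12.5.1 names only ANOVA and lists no covariates. SAP section 4 notes that the BCVA categories match the core study's SAP. No reason is given for the age or CSFT cuts.

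**The concern.** Change in thickness usually depends on starting thickness, so the baseline value is the covariate that matters most in the CSFT model. A two-level factor treats all eyes below 400 µm as alike. After 64 weeks of treatment in the core study, few eyes may lie above the cut, and the factor would then carry little information.

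Two things are at stake. The first is precision: variance that the measured baseline could explain stays in the residual. The second is adjustment. CSFT change is reported for all participants and per core arm, and data on switching from aflibercept are a stated purpose (protocol 1.2). Protocol 4.2 describes brolucizumab as better than aflibercept on fluid control in two earlier trials, so the core arms may differ in CSFT at extension baseline. A model that already sets out to adjust for baseline CSFT would then remove only part of that difference, and readers comparing the arms would not know how much.

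**Working it through.** **The plan's own figure.** For mean BCVA change the interval is −1 ± t(0.975, n−1) × 13/√n. With n = 250 this gives −1 ± 1.62, or (−2.62, 0.62). The documents state (−2.6, 0.62), so it reproduces. It uses the raw SD of 13 with no covariates and does not depend on the categories. The documents give no corresponding figure for CSFT.

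**Inputs.** The cuts come from SAP 2.2.1 and 2.3. Baseline distributions, correlations and a 125/125 split by core arm are assumptions, because the documents give none.

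**Share of baseline variance kept by one cut.** For a normal covariate with a proportion p above the cut at z, the share kept is k = φ(z)² / [p(1−p)]. To first order, 1−k is the share of an arm difference left unadjusted.

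| Eyes ≥ 400 µm | z | φ(z) | k | 1−k |
|---|---|---|---|---|
| 3% | 1.881 | 0.068 | 0.16 | 0.84 |
| 5% | 1.645 | 0.103 | 0.22 | 0.78 |
| 10% | 1.282 | 0.175 | 0.34 | 0.66 |
| 20% | 0.842 | 0.280 | 0.49 | 0.51 |

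Over a wider range (mean CSFT 250 to 450 µm, SD 60 to 150), k runs from 0.05 to 0.64. The maximum occurs when the cut falls at the mean.

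**Residual variance.** Let ρ be the correlation of baseline with follow-up CSFT. With equal SDs, R² of change on baseline is (1−ρ)/2, and the ratio of residual variances (categories to continuous) is (1 − kR²)/(1 − R²).

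- ρ = 0.5, 5% above the cut: (1 − 0.224 × 0.25)/0.75 = 1.26
- ρ = 0.8, 20% above the cut: (1 − 0.49 × 0.10)/0.90 = 1.06

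The range is thus 6% to 26% more residual variance. In interval width that is √1.06 = 1.03 to √1.26 = 1.12, or 3% to 12% wider. In participants it is like losing 1 − 1/1.06 (about 5%) to 1 − 1/1.26 (about 21%).

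**Effect on an arm comparison (illustration).** Take a 20 µm baseline difference, baseline SD 80, SD of change 60 and correlation of baseline with change −0.5. The slope is −0.5 × 60/80 = −0.375, so 20 × −0.375 = −7.5 µm of the arm difference in change goes with the baseline difference. The simulation used 125 per arm and 2,000 runs.

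| Mean CSFT (µm) | k | (1−k) × −7.5 | Simulated, two categories | Simulated, continuous |
|---|---|---|---|---|
| 275 | 0.249 | −5.6 | −5.5 | 0.1 |
| 300 | 0.353 | −4.9 | −4.5 | 0.3 |
| 350 | 0.552 | −3.4 | −3.5 | −0.1 |

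**BCVA and age.** With mean BCVA 60 to 75 and SD 10 to 20, the three categories keep 68% to 81% of the variance. Suppose baseline and change correlate at 0.3 in absolute value, so R² = 0.09. For k = 0.75 the variance ratio is (1 − 0.75 × 0.09)/0.91 = 1.025, and the interval is about 1.2% wider. For k = 0.81 it is about 0.9% wider. The two age categories keep 53% to 64% (mean age 73 to 80, SD 7 to 9).

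**The case against.** The strongest reply has five parts.

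- **The protocol chose categories for BCVA.** A reader might infer from the protocol summary that continuous covariates were intended and the SAP departs from them. The documents do not support that: section 12.4.2 and Table 12-1 specify categories, and the summary is shorthand. Matching the core study is a legitimate reason for the BCVA cuts. This stands for BCVA; no such reason is offered for CSFT.
- **The primary result is barely touched.** A reader might infer that the primary BCVA estimate suffers materially. It does not. It is a one-arm mean, three categories keep most of the variance, and the planned precision does not rest on the covariates. This stands.
- **Per-arm results are secondary.** No between-arm test is planned, SAP 2.6.1 promises summary statistics, and SAP 2.3 tabulates baseline CSFT by core arm, so an imbalance will be visible. This limits the consequence. But SAP 2.6.2 attaches model-based intervals to these results, and that model is the one at issue.
- **The residual is not necessarily an artefact.** A reader might infer that greater thinning in a thicker aflibercept arm would be regression to the mean alone. The documents do not establish that. Extension baseline is core Week 64, after randomisation, so a difference there may partly be a treatment effect, and later thinning may be a real effect of switching. This stands and governs interpretation. It does not justify an adjustment that is only partial.
- **The 400 µm split is an inference, and the sizes rest on assumptions.** Both are true. SAP 2.6.2 does not define its categories, and the share kept ranges widely. Categories also avoid a linearity assumption, but that assumption can be checked.

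**Conclusion.** The point holds for the secondary CSFT model. If the categories are the 400 µm split, 51% to 84% of a core-arm difference in baseline CSFT stays unadjusted when 3% to 20% of eyes lie above the cut (36% to 95% under the wider assumptions). Residual variance is about 6% to 26% larger than with the continuous value. These figures rest on a normal distribution and on shares, correlations and an arm split that the documents do not give.

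For BCVA the loss is small, about 1% of interval width at a correlation of 0.3 between baseline and change. The planned sample-size precision is unaffected. This is a worthwhile improvement to a secondary analysis and does not undermine the primary conclusions.

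**What to change.** - **CSFT model (SAP 2.6.2).** Use continuous extension-baseline CSFT and continuous age with core arm, and check linearity with a quadratic term or a spline. Keep the CSFT categories for display or a supportive model, and define them in 2.6.2 if they stay in any model.
- **BCVA models (SAP 2.5.2, 2.5.4, Table 2-1).** Either add a supportive model with continuous BCVA and age, or make it the main model and record that in SAP section 4 as a change from protocol 12.4.2 and Table 12-1. The gain is small either way.
- **Reporting.** Give unadjusted per-arm changes beside the adjusted ones. State that extension baseline is after core randomisation, and do not attribute any residual difference to regression to the mean alone.

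No new data are needed. For CSFT the cost is SAP wording before database lock, since protocol 12.5.1 does not prescribe categories. The downsides are an assumption of approximate linearity and, if the main BCVA model is changed, a departure from the core study's categories.

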2.3 Patient disposition, demographics and other baseline characteristics

Demographic and other extension study baseline data including disease characteristics will be summarized by appropriate descriptive statistics for all analyses sets. A listing will also be provided.

A baseline (of the extension study) disease characteristic table will be provided by treatment groups of the core study and overall, including:

- Primary diagnosis of nAMD, time since diagnosis of nAMD (days), whether nAMD is unilateral or bilateral and intraocular pressure (IOP).
- BCVA (as a continuous variable and using categories (< 55, 55-< 73, ≥ 73 letters read)),
- OCT angiography parameters – if collected.
- SD-OCT parameters (IRF, SRF, sub-RPE, CSFT (as a continuous variable and using categories (< 400, ≥ 400 μm)) and lesion type).
- CFP parameters (intra-retinal hemorrhage – central subfield, sub-retinal hemorrhage – central subfield, RPE atrophy – outer subfield, RPE atrophy – central subfield, fibrosis – inner subfield, fibrosis – central subfield).
- FA parameters (type of CNV, area of CNV within the lesion, CNV location, leakage from CNV).

Relevant medical histories and current medical conditions at baseline of the extension study will be summarized separately by system organ class and preferred term for the FAS.

Medical history/current medical conditions will be coded using the latest version of Medical Dictionary for Regulatory Activities (MedDRA) terminology available at the time of the analyses. The MedDRA version used for reporting will be specified in the clinical study report (CSR) and as a footnote in the applicable tables/listings.

Medical histories which started before the core study and are ongoing on Day 1 of the extension study will be recorded on the Medical History eCRF. Data collected for the Medical History

eCRF for the extension study will be presented by the treatment arm in the core study and overall. Columns will be included to identify if the event started before the core study, during the core study, or during the extension study; and if the event is ongoing or ended during the Extension study.

2.3.1 Patient disposition

Patient disposition for all participants will be summarized based on the Enrollment Set. A listing will also be provided.

The number (%) of participants in the FAS and PPS will be presented based on the Enrollment Set. Participants excluded from the FAS and PPS including the corresponding reasons will be presented in a listing.

A listing of all important protocol deviations with their respective deviation/restriction categories will be provided. A summary table for PDs will also be provided (if appropriate). The number and percentage of participants with important PDs will be presented by deviation/restriction category. Due to the COVID-19 pandemic, a higher number of PDs are expected. To evaluate the PDs occurring due to the COVID-19 pandemic, the number and percentage of participants with PDs occurring due to the COVID-19 outbreak will also be provided by deviation category. A listing of PDs will be provided by participant, including the relationship to COVID-19, and the information if the PD led to exclusion of the participant from an analysis set.

2.4 Treatments (study treatment, rescue medication, concomitant therapies, compliance)

2.4.1 Study treatment / compliance

The FAS will be used for the analyses below.

2.4.2 Prior, concomitant and post therapies

Concomitant medications and significant non-drug therapies prior to and after start of study treatments will be summarized according to the Anatomical Therapeutic Chemical (ATC) classification system based on Enrollment Set.

Medications taken at least once during the extension study and medications started on the end of study visit date for the core study/extension study baseline visit date will be recorded on the Concomitant Medications eCRF.

Prior medications (ocular and non-ocular) will be summarized using number and percentage of patients by ATC class and PT according to the World Health Organization (WHO) drug reference list directory. Prior ocular medications will be summarized overall and separately for

the study and fellow eye; and by the treatment arm in the core study. Prior medications are those that have a start date prior to the date of the first administration of study treatment in this extension study.

A concomitant medication is defined as any medication taken at least once after the first administration of study treatment in this extension study. Concomitant medications will be summarized.

Procedures occurring during the extension study and procedures occurring on the end of study visit date for the core study/extension study baseline visit date will be recorded on the Procedures eCRF.

Prior surgical and medical procedures are those that have a start date prior to the date of the first injection of study treatment in this extension study.

2.5 Analysis of the primary objective

The primary objectives of the study are:

- To evaluate the extended durability of brolocizumab in a TtC regimen with respect to the duration of treatment intervals up to Week 56.
- To evaluate the functional outcomes of brolocizumab in a TtC regimen with respect to average change in BCVA at Week 52 and Week 56, i.e., change from the extension study baseline to the average of Week 52 and Week 56.

2.5.1 Primary endpoint

The primary endpoints of the study are:

- Duration of the last interval with no disease activity up to Week 56.
- Average change in BCVA from baseline of the extension study at Week 52 and Week 56.

Primary estimands along with the sensitivity estimands are shown in [Table 2-1](#).

2.5.2 Statistical hypothesis, model, and method of analysis

The average change in BCVA from baseline of the extension study at Week 52 and Week 56 will be estimated by an analysis of variance (ANOVA) with baseline age categories, baseline BCVA categories and treatment arm in the core study included as fixed effects. The estimate of BCVA change will be accompanied by the 95% CI.

For the analysis of durability, the first step is to identify the last (treatment) interval with respect to Week 56 for each participant, i.e. the last interval for which injections have occurred at both ends of this interval before/at Week 56. If there is disease activity at the end of the last interval, then the last interval will be shortened by 4 weeks, down to a minimum of q4w. Subjects who do not receive any injection (or only one injection) of study drug in the extension study will be excluded from this analysis. In case of any treatment interruption or permanent study treatment discontinuation, the imputation techniques as per the estimand framework in [Section 2.5.3](#) will be considered. Then, the proportion of participants with last interval of q4w, q8w, q12w, q16w, and q20w will be specified. These proportions will be referred as the distribution of the last interval.

The distribution of the last interval with no disease activity up to Week 56 will be described based on counts and proportions of participants at 4-week, 8-week, 12-week, 16-week, and 20-week intervals. These proportions will be accompanied by 95% CIs. The counts and proportions will be accompanied by 2-sided 95% CIs inferred based on binomial distribution for each endpoint and 2-sided 95% simultaneous CIs inferred using the Goodman method (Goodman 1965). The Goodman method is used for obtaining simultaneous CIs for the parameters of a multinomial distribution, for example for a multinomial endpoint (4-week interval, 8-week interval, 12-week interval, 16-week interval, and 20-week interval).

